DSMRC	Defence Services Medical Research Centre, Myanmar Ministry of Defence	OCRA	Office of Clinical Research Affairs, DMID, NIAID, NIH, DHHS
ERC	Ethics Review Committee	OHRP	Office for Human Research Protections
FWA	Federal-Wide Assurance	ORA	Office of Regulatory Affairs, DMID, NIAID, NIH, DHHS
GCP	Good Clinical Practice	PI	Principal Investigator
GMS	Greater Mekong Sub-Region	RDT	Rapid diagnostic test for malaria
HIPAA	Health Insurance Portability and Accountability Act	RIP	Research information portal

List of Abbreviations

icddr, b	International Centre for Diarrhoeal Disease Research, Bangladesh	sFTP	Secure file transfer protocol
ICF	Informed Consent Form	SMC	Safety Monitoring Committee
ICH	International Conference on Harmonisation	SOP	Standard Operating Procedure
IEC	Independent or Institutional Ethics Committee	usPCR	Ultrasensitive polymerase chain reaction
IRB	Institutional Review Board	WHO	World Health Organization

PROTOCOL SUMMARY

Title:	Preliminary Study of Subclinical Malaria
Population:	Up to 6,000 residents of all ages in villages, refugee camps, military bases, and work sites, including children, pregnant women, and the elderly; the number of participants screened to achieve enrollment ceiling is not known
Number of Sites:	Up to 6 (each with at least 2 villages, towns, unions, refugee camps or plantations, or a single military base)
Study Duration:	Up to 1.5 years
Subject Duration:	Up to four months (military population may be under observation up to 4-6 weeks)
Ethical Oversight:	Ethics Review Committee (ERC), Department of Medical Research (DMR), Myanmar Ministry of Health and Sports (MoHS) Institutional Review Board (IRB), Defence Services Medical Research Centre (DSMRC), Myanmar Ministry of Defence IRB, International Centre for Diarrhoeal Disease Research (icddr,b), Bangladesh IRB, National Institute of Parasitic Diseases (NIPD), Chinese Center for Disease Control and Prevention (China CDC) IRB, Duke University Health System

Study Objectives:**Primary objective:**

Make a preliminary assessment of the dynamics of subclinical malaria detected by ultrasensitive PCR to guide the design of a matched cohort study of subclinical malaria in Myanmar and along its borders with China and Bangladesh

(The objective of the subsequent matched cohort study, to be reviewed as a separate protocol, will be to compare the incidence of clinical malaria and malaria transmission capacity, in participants with and without subclinical malaria.)

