2.4.1. Preliminary study

In this study, a small number of asymptomatic infections detected by ultrasensitive PCR (usPCR) will be followed and tested intensively for three months to measure the temporal dynamics of these infections. A much larger number of uninfected individuals will be followed

for just 2-4 weeks (two visits), providing a comparator group for the infected cohort. The validity of our results in a subsequent matched cohort study depends, in part, on our ability to accurately classify infection status using a single usPCR result. In other words, do we have sufficient confidence in the correct classification of malaria infection positive and negative status using usPCR test at the beginning of the study? While there is no gold standard test more sensitive than usPCR, repeated usPCR testing offers a surrogate. Presumably, in a low transmission setting, someone who is truly uninfected on the first testing should remain negative on multiple consecutive tests, but this remains to be confirmed.

If this initial evaluation confirms that usPCR results are relatively stable - i.e., that most usPCR+ infections remain positive on most or all repeated testing over the course of three months, and that most usPCR- infections remain negative upon re-testing 2-4 weeks later, then we can move forward with the cohort study with confidence that our initial classification of exposure is a meaningful basis for assessing subsequent outcomes. If, however, a single usPCR result is found to be "unstable", we may need to consider testing at least twice before assigning infection status. Similarly, we may wish to increase the sample size if we determine that the sensitivity and specificity of a single usPCR test (compared to results of multiple testing) is high enough to proceed with single testing at screening and enrollment, but lower than ideal (e.g. sensitivity/specificity 50-75%).

2.4.2. Design of the subsequent matched cohort study (to be submitted for ethical review later as a separate protocol)

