4. STUDY DESIGN

4.1. Overview

- Prospective, multi-site short longitudinal study
- Up to six study sites, each with >2 villages, towns, unions, refugee camps or plantations, or a single military base. Alternative and additional sites may be added to ensure enough infected cases.
- Screening for eligibility (age at least 0.5 year; able & willing to strictly follow study protocol and to provide written informed consent or assent as appropriate)
- Enroll and consent eligible individuals
- RDT-positive: one-time enrollment for data and venous blood collection; Refer to and ensure appropriate treatment by care providing team; No study-related follow up
- RDT-negative: Collect data and DBS samples; Return to research clinic in 2-4 weeks
- PCR-negative participants: One follow up visit approximately 2-4 weeks after enrollment
- PCR-positive participants: Five follow up visits at approximately 4, 6, 8, 10, and 12 weeks (for those with total 12 weeks follow up) or 2, 3, 4, 5 and 6 weeks (for those with total 6 weeks follow up) after enrollment
- Total up to 6000 residents in up to six study site of all ages in villages, refugee camps, military bases, and work sites are to be enrolled
- Finger stick blood sampling will be done for RDT and dried blood spot sampling in all participants at each scheduled and unscheduled visit.
- Venous sampling will be done for participants with RDT+ infections detected at times when study staff trained for venous sampling are present. Blood volumes at any time point are limited to 2 mL for children aged < 3 years, 3 mL for age 3-5 years, and 5 mL for older children and adults.
- Estimated duration of study: 18 months

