6.1.3. Follow-up

All enrolled participants will follow up 2-4 weeks after enrollment. Those who are found to be usPCR negative will provide one additional DBS at a second visit at 2-4 weeks and discharged from the study. Those who are found to be usPCR positive will provide four additional DBS, two weeks apart (weeks 6, 8, 10, and 12), and discharged from the study at Week 12. For the military population who are likely able to provide a total of only 6 weeks follow up, they will return at 2 weeks after enrollment, and the follow up schedule will be weekly.

At each follow up visit, a brief history (including travel history update) will be taken, and dried blood spots will be collected. Those who miss two consecutive follow-up visits will be

discharged from the study. At any time that participants are found to be RDT+, if study personnel qualified to collect venous blood are present, RDT+ participants will provide venous blood for serology and parasite nucleic acid sequencing. Individuals testing RDT+ at any time during the study will be referred for prompt ACT treatment of malaria by local health providers.

Conceptual framework of the study is shown below:

Anticipated duration of screening and enrollment phase: Screening and enrollment will begin at each site after obtaining ethical approval from all relevant administrative and ethical review committees for that site. Because technical capacity for usPCR is not yet established at the China and Bangladesh sites, the study is expected to begin sooner at the Myanmar sites. Screening will be continued until enrollment targets are reached.

Duration of follow-up for each subject: Up to 4 months (~2-4 weeks initial assessment plus up to 1.5-3 months follow-up).

Total study duration: Up to 1.5 years

Retention: We have achieved retention rates of >95% in longitudinal cohort studies in Madaya (unpublished) and Bandarban [54-58] by maintaining strong relationships with the community, including regular community meetings; contributing to community welfare through training health providers and upgrading facilities; and treating informed consent as an ongoing process for the individual and the community [59, 60]. Retention is expected to be lower at sites with refugees and military troops, requiring additional screening at those sites, as noted above.

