Study termination: Participants will end their participation in the study when they miss two or more consecutive follow-up visits. Participants who return after more than two consecutive missed visits will be eligible to be re-screened and re-enrolled as a new participant.

Study visit schedule and primary evaluations: Active surveillance will consist of scheduled visits every 1-2 weeks for procedures shown in Table 2a and 2b. Passive surveillance will be conducted by encouraging participants to see the local health provider when ill. Local providers will collect dried blood spot samples whenever RDTs are done and will notify study staff of positive tests so that venous blood can be collected. In accord with WHO and NMCP policies in all three countries, any positive RDT result, whether testing was done as part of active or passive surveillance, will result in referral for ACT treatment, which will be administered by local providers as routine care and not as part of the study.

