7.4. Analysis Plan

Primary analysis will compare the proportion of individuals with initially positive usPCR tests that were followed by 1 or more consecutive positive tests on biweekly testing. Using the screening results, we will also calculate the proportion of individuals with negative usPCR tests that subsequently had usPCR positive tests at the second screening test.

Secondary analyses will include comparisons based on incidence of species-specific RDT+ and usPCR+, and, for serological studies, breadth (% seropositivity) and magnitude (mean fluorescence intensity) of antibody responses on protein and peptide microarrays.

To understand the dynamics of usPCR positivity, we will construct maximum likelihood models using Markov chains to evaluate risk factors that increase or decrease the probability of going from state to state between monthly sampling time points.

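### The Markov model in Section 7.4 assumes monthly steps, but usPCR-positive participants are mostly sampled 1 or 2 weeks apart, and the plan does not say how unequal gaps are handled

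*Combined protocol and SAP*

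**What the plan says.** Section 7.4 describes the model for usPCR dynamics in one sentence: maximum likelihood Markov chains to study risk factors that change the "probability of going from state to state between monthly sampling time points". It does not say whether time is discrete or continuous, how unequal gaps enter the likelihood, or whether visits are thinned to a grid.

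The schedules for usPCR-positive participants are in Section 4.1 and Tables 2a and 2b. The longer one is "Five follow up visits at approximately 4, 6, 8, 10, and 12 weeks"; the shorter is "2, 3, 4, 5 and 6 weeks (for those with total 6 weeks follow up) after enrollment". Section 6.1.3 assigns the shorter one to the military population: "they will return at 2 weeks after enrollment, and the follow up schedule will be weekly". The Protocol Summary adds that the "military population may be under observation up to 4-6 weeks". Section 6.1.3 also states: "Active surveillance will consist of scheduled visits every 1-2 weeks for procedures shown in Table 2a and 2b".

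Two further provisions make the gaps less regular. Sections 6.1.1 and 6.1.3 allow the first return visit at 2 to 4 weeks. And Section 6.1.3 says: "Participants will end their participation in the study when they miss two or more consecutive follow-up visits". One isolated missed visit therefore lengthens a gap while the participant stays in the study.

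**The concern.** A discrete-time chain needs every step to cover the same time. Here the steps differ within a schedule, and between schedules by a factor of two at each visit position. The plan does not say which rule applies, so the analyst must choose one, possibly after seeing the data.

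The schedule is not assigned at random. The military is the only group named for the weekly schedule. Section 4.1 defines a site as several villages or similar units, or a single military base, so schedule also follows site. Any covariate that differs between these groups can pick up the effect of gap length. The same problem reaches the preliminary chronicity estimate listed as a secondary objective in Section 7.1: a per-step probability is not a monthly one.

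**Working it through.** **Plan's own figure.** Section 7.2 gives 6 observations per usPCR-positive participant. One enrolment sample plus five follow-ups gives 6 on either schedule, so the figure reproduces.

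**Gaps.**
- 12-week schedule, weeks 0, 4, 6, 8, 10, 12: gaps 4, 2, 2, 2, 2 (mean 12/5 = 2.4 weeks). One gap in five is about a month.
- 6-week schedule, weeks 0, 2, 3, 4, 5, 6: gaps 2, 1, 1, 1, 1 (mean 6/5 = 1.2 weeks). None is a month.
- First return at week 2 on the 12-week schedule: gaps 2, 4, 2, 2, 2.

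**Assumptions.** The documents give no clearance rate and no assay accuracy estimate. I assume the same true process in both groups, all infected at week 0, and median duration 4, 8, 12 or 26 weeks. Four-week clearance is 1 − 2^(−4/median) = 50%, 29%, 21%, 10%. Rows with an imperfect test add specificity 0.99 and reacquisition of 2% per 4 weeks.

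**Reading 1: each visit-to-visit move is one step.** With a perfect test and no reacquisition, S(t) = 2^(−t/median), and the per-step loss probability is [1 − S(last visit)] divided by the sum of S over the visits that start a step. For a median of 8 weeks:
- 12-week: (1 − 0.3536)/(1 + 0.7071 + 0.5946 + 0.5000 + 0.4204) = 0.6464/3.2222 = 0.201
- 6-week: (1 − 0.5946)/(1 + 0.8409 + 0.7711 + 0.7071 + 0.6484) = 0.4054/3.9675 = 0.102
- Odds ratio, military/non-military: (0.102/0.898)/(0.201/0.799) = 0.45

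Across the assumed range:

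| Sensitivity | Median 4 wk | 8 wk | 12 wk | 26 wk |
|---|---|---|---|---|
| 100% (specificity 1, no reacquisition) | 0.40 | 0.45 | 0.47 | 0.49 |
| 90% | 0.49 | 0.61 | 0.67 | 0.79 |
| 75% | 0.57 | 0.72 | 0.79 | 0.89 |
| 50% | 0.65 | 0.80 | 0.86 | 0.93 |

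Every entry should be 1. On the 12-week schedule, missing one interim visit gives an odds ratio of 1.14 to 1.55 against full attenders (perfect test).

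**Chronicity under reading 1.** At a median of 8 weeks the true 4-week clearance is 29%. The step estimates are 20% (12-week) and 10% (6-week) with a perfect test, but 41% and 33% at sensitivity 75%. The error has no fixed direction.

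**Reading 2: only 4-week points are kept.** Weeks 0, 4, 8, 12 leave 3 of 5 transitions; weeks 0 and 4 leave 1 of 5. So 2 of 5 and 4 of 5 are discarded. If all are infected at week 0, the military odds ratio is 0.99 to 1.00. That depends on the assumption. With specificity 0.99 and 5% prevalence in both groups (assumed), it is 1.08 to 1.44 at sensitivity 50% to 90%.

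**The shared week 0 to 4 interval.** The share of baseline positives truly infected is πSe/[πSe + (1 − π)(1 − Sp)], where π is prevalence. With Se = 0.90 and Sp = 0.99 this is 0.045/0.0545 = 0.826 at 5% prevalence and 0.090/0.099 = 0.909 at 10%. At a median of 26 weeks, a truly infected baseline positive tests negative at week 4 with probability 0.189, and an uninfected one with probability 0.973.
- 5%: 0.826 × 0.189 + 0.174 × 0.973 = 0.326
- 10%: 0.909 × 0.189 + 0.091 × 0.973 = 0.260
- Odds ratio, lower over higher prevalence: (0.326/0.674)/(0.260/0.740) = 1.37

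Over the same medians and sensitivities of 50% to 90%, the range is 1.16 to 1.37, with identical dynamics.

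**The case against.** The study is largely descriptive (Section 2.3). Monthly may be a leftover word, and a competent analyst would probably use visit dates. Nor is the word wholly wrong: the first gap in Table 2a is 4 weeks, and the usPCR-negative retest is about monthly when done at week 4. The larger distortions come from reading 1, which fits the word monthly less well than reading 2. All sizes rest on assumed durations and test accuracy. Section 2.4.1 does entertain single-test accuracy "but lower than ideal (e.g. sensitivity/specificity 50-75" per cent, but as a hypothetical against repeated testing, which mixes clearance with test error. It is not an estimate of per-test sensitivity.

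These points limit the weight of the concern without removing it. The written step is wrong for most transitions, and either way of applying it costs something: bias under reading 1, lost data under reading 2.

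A reader might go further and infer that the plan will report a false military effect, or false effects of occupation and travel. The documents do not support that. No military contrast is planned, Section 7.4 names no covariate for this model, and the objective that mentions occupation and travel concerns clinical malaria and transmission capacity. On the initial site list the Defence Services partner has one location (Figure 3), so military status could not be separated from site under any handling of gaps.

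A reader might also take the week 0 to 4 interval as a clean basis for comparing the groups. It is not: with imperfect specificity it depends on baseline prevalence, and the 2-to-4-week window means a week-4 sample is not guaranteed.

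**Conclusion.** The concern holds. The monthly step in Section 7.4 does not describe the sampling of usPCR-positive participants, and the handling of unequal gaps is unspecified. Treating moves as equal steps biases any covariate tied to schedule or site. For military status the false odds ratio is about 0.40 to 0.49 with a perfect test and 0.49 to 0.93 at sensitivity 90% to 50%, given equal true dynamics, all infected at week 0, median duration 4 to 26 weeks, specificity 0.99 and reacquisition 2% per 4 weeks (the last two for the imperfect test only). Thinning to 4-week points discards 40% of transitions on one schedule and 80% on the other.

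The damage is confined to the secondary dynamics and chronicity estimate and to this model's risk-factor results. It would be tempting to extend it to the primary outcomes, but those are simple proportions that do not come from the Markov model. The correction is worth making before analysis.

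**What to change.** Replace the sentence in Section 7.4 with:

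> Transitions between usPCR states will be modelled with a continuous-time (panel-data) Markov likelihood using the actual days between consecutive DBS collections. Transition probabilities will be reported per 4 weeks and by schedule, and risk-factor models will be stratified by schedule or site. A sensitivity analysis will allow for usPCR misclassification where identifiable.

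The sensitivity analysis is needed because false negatives arise per test, not per week, so closer testing can look like faster clearance even when actual gaps are used.

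Add that any military versus non-military difference is confounded with schedule and site and is descriptive only. Do not designate the week 0 to 4 contrast as free of bias.

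The cost is one paragraph, a recorded collection date for each blood spot, and slightly more analysis work. The misclassification model may be weakly identified, and the plan should say so. Visits and sampling do not change.

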8. SUBJECT CONFIDENTIALITY

Subject confidentiality is held strictly in trust by the participating investigators and their staff. This confidentiality is extended to cover testing of biological samples, in addition to the demographic information relating to participating subjects. The study protocol, documentation, data and all other information generated will be held in strict confidence. Study records including case record forms and consent forms will be stored in locked cabinets in secure facilities only accessible to authorized investigators, and/or in password-protected devices and computers.

All participants will be assigned a unique study identification (ID) number. This number will be used to label all biologic samples and study-related documents except informed consent/assent forms which will contain the participant's identifier and will be stored in secured space as described below. All data generated from each study sample will be linked to the coded, unique ID and associated study data.

Study data will be stored on password protected computers at the study site under the purview of leadership of the DMR, DSMRC, icddr,b and NIPD, with restricted access to specified study personnel. Genetic/genomic data generated from malaria parasites isolated from study participants may be submitted to publicly available databases, but will not be linked to any identifying information from study participants. Participants will not be identified in any publications resulting from the study.

The data will be used by the PI and study collaborators to assess parasite gene flow and genotype candidate markers of drug resistance as described in this document. The data will be stored in secure, password-protected databases at the malaria laboratories at the Duke University in Durham NC for up to 20 years, after which the data may be destroyed.

8.1. Future Use of Stored Specimens

All study participant will be asked whether we will be permitted to use left-over blood sample for future studies 1) related to malaria; 2) related to any infections or 3) related to any diseases. Studies of microbial RNA or DNA (chiefly malaria, but also other infectious agents that may explain non-malaria fevers) derived from samples may be done without restriction. Studies of human RNA or DNA using archived samples or material will be done only if specific permission for additional such studies is obtained from the relevant IRBs. Study participants will have the right to withdraw their permission for further use of their samples at any time during and after the study. Specimens will be maintained in malaria laboratories at the DMR, DSMRC, NIPD, icddr,b and/or Duke University. Specimens will be labeled with a coded, unique identifier and will not contain identifying information.

9. INFORMED CONSENT PROCESS

The principles of informed consent in the current edition of the Declaration of Helsinki will be implemented before any protocol-specified procedures are carried out.

Information about the study will be given to prospective participants in both oral and written forms whenever possible. The written consent documents will embody the elements of informed consent as described in the current edition of the Declaration of Helsinki, will adhere to the ICH Harmonized Tripartite Guideline for Good Clinical Practice and 45CFR46 and 21CFR50, and will also comply with applicable Myanmar regulations. The oral consent process will be consistent with 45CFR46.846.117, 21CFR50.27 and ICH E6 (R1) Section 4.8. Independent witnesses will be used to attest that illiterate potential participants have understood the contents of the informed consent document.

9.1. Informed Consent/Accent Process (in Case of a Minor or Others Unable to Consent for Themselves)

We have published detailed descriptions of the processes we use to obtain community “permission to enter” and individual informed consent [60]. We consider informed consent to be a dynamic, ongoing process, with continuous availability of investigators to answer any questions that arise in the course of the study and to ensure that participants and their parents/guardians understand study procedures. These same principles will be followed in this study. All NMCPs in the GMS routinely conduct multiple annual therapeutic efficacy surveys to monitor efficacy of ACT. As a result, communities throughout the GMS have now become familiar with the informed consent process, including written, signed consent forms, which used for NMCP therapeutic efficacy surveys. The investigators will work with local research staff at each site to assure study information and informed consent procedures meet requirements of the community and the local IRBs.

Since the vast majority of study participants’ parents/guardians do not use telephones, fax, or mail, contact information is provided in terms of local physicians who can be visited directly and who can themselves reach the investigators directly or by telephone or fax.

Individuals who are at least 18 years old are considered adults and will provide consent for themselves; children aged up to 12 years will provide verbal assent in addition to written consent provided by their guardians; children aged 13–17 years will provide written assent in addition to written consent provided by their guardians. Guardians need not necessarily be the child’s parent(s). Any close relative including aunts, uncles, grandparents, adult siblings etc. who accompany the child to the clinic may serve as the guardian for the sake of providing informed consent. This may include neighbors or village elders in the case of orphans.

